### 4.3.1 Analysis Window

For visits that occur on or after the first dose of study treatment, study day is defined as date of event – date of first dose of study treatment + 1. For visits that occur prior to the first dose of study treatment, study day is defined as date of event – date of first dose of study treatment. There is no study day 0 defined for this study.

**Table 1. Analysis Window for Safety Parameters**

Nominal Visit	Analysis Visit	Target Study Day	Minimum Study Day	Maximum Study Day
Visit 2	Baseline	1	-30	1
Visit 3	Week 1	8	2	11
Visit 4	Week 2	15	12	18
Visit 5	Week 4	29	26	32
Visit 6	Week 6	43	40	46
Visit 7	Week 8	57	54	60
Visit 8	Week 10	71	68	74
Visit 9	Week 12	85	82	88
Visit 10	Week 14	99	96	102
Visit 11	Week 16	113	110	116
Visit 12	Week 18	127	124	130
Visit 13	Week 20	141	138	144
Visit 14	Week 22	155	152	158
Visit 15	Week 24 (End of Treatment)	169	166	172
Visit 16	Week 28	197	192	202
Visit 17	Week 32 (End of Study)	225	220	230

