6.19 Early Termination Visit

Should a patient withdraw consent or be withdrawn from the study for any reason after randomization, every effort should be made to schedule a final visit, during which the following assessments and procedures should be completed in the order given below, if possible:

- Review and recording of changes in concomitant medications
- Vital sign measurements
- Body weight recorded
- CT scan (only required for subjects that are enrolled at Study Sites that are approved and qualified to perform CT Scans)
- NCS assessment
- EQ-5D-5L questionnaire
- VAS-rhinosinusitis assessment
- SNOT-22 assessment
- TNSS assessment
- UPSIT assessment of smell
- Nasal endoscopy and NPS scoring
- Pulmonary function tests (Spirometry) for patients with comorbid asthma only
- Healthcare resource utilization questionnaire
- Complete physical examination
- 12-lead ECG
- Urine pregnancy test
- Safety laboratory samples (hematology, serum chemistry, urinalysis)

- PK blood sample
- PD blood sample
- ADA blood sample
- Collect the daily patient handheld device
- AE review and recording

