#### 4.12.4 Clinical Laboratory Evaluation

All laboratory values will be reported and summarized using standard international (SI) units ([Appendix D – Laboratory SI U](#)). CTCAE v5.0 will be used for the laboratory toxicity grade ([Appendix E: CTCAE V5.0 Toxicity Grading for Laboratory Parameters](#)).

The following central laboratory tests will be summarized:

- Hematology: red blood cell count, hemoglobin level, hematocrit level, white blood cell count with differential, and platelet count
- Serum Chemistry: blood urea nitrogen (BUN), creatinine, uric acid, total bilirubin, sodium, potassium, calcium, chloride, bicarbonate, alkaline phosphatase (ALP), aspartate aminotransferase (AST), alanine aminotransferase (ALT), lactate dehydrogenase (LDH), gamma-glutamyltransferase (GGT), creatine phosphokinase (CPK), albumin, total protein, total cholesterol, triglycerides, C-reactive protein (CRP), and glucose
- Urinalysis: pH, protein, glucose, ketones, bilirubin, blood (hemoglobin), urobilinogen, nitrites, leukocytes, and specific gravity; microscopic analysis if abnormal

Continuous test results for each parameter and changes from baseline will be summarized at each visit by treatment and overall using descriptive statistics. Categorical test results for each parameter will be summarized at each visit by treatment and overall using frequencies and percentages. Shift of laboratory toxicity grade from baseline to each post-baseline visit will be summarized by treatment and overall. By-subject listings of laboratory parameters will also be provided.

Laboratory values will be listed by subject and study time point including changes from baseline, where available. All values outside the clinical reference ranges will be flagged in the data listings. The abnormal values will be flagged with 'L' for values below the lower limit of the clinical reference range and 'H' for values above the upper limit of the clinical reference range and included in the listings.

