#### **4.15 Changes in the Conduct of the Study or Planned Analysis**

Enrollment of Sponsor's Phase 2 trial evaluating CBP-201 in chronic rhinosinusitis with nasal polyps, which commenced in June 2021, has faced challenges due to the macroenvironment -- namely ongoing impact of COVID and the current Russia-Ukraine conflict throughout [Eastern] Europe.

Therefore, the Sponsor has made the decision to terminate this trial early, and the planned analyses have been changed to focus on safety assessments.

For the efficacy endpoints, only descriptive summary statistics will be provided for the co-primary efficacy assessments. No formal hypotheses will be tested due to the small sample size. No sensitivity or subgroup analyses will be performed. All other efficacy assessments will be listed except percentage of maxillary sinus volume occupied by disease on CT and Lund-Mackay Computed Tomography scores.

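### The safety analysis windows leave gaps and have no early-termination rule, so off-schedule results fall out of the by-visit safety summaries

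*SAP*

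**What the plan says.** SAP 4.3.1 assigns safety results to visits by study day. Under "Table 1. Analysis Window for Safety Parameters" the rows run, in the order target, minimum, maximum: "Visit 3 Week 1 8 2 11", "Visit 4 Week 2 15 12 18", "Visit 5 Week 4 29 26 32", and so on every two weeks to "Week 24 (End of Treatment) 169 166 172". Week 28 covers Days 192 to 202 and Week 32 covers Days 220 to 230. No row is given for early termination.

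Two further rules follow SAP Table 5. When several results share an analysis visit, the one nearest the target day is used. An unscheduled result is used only when the scheduled one is unavailable.

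The tables that depend on these windows are by visit. For laboratory data, SAP 4.12.4 says: "Continuous test results for each parameter and changes from baseline will be summarized at each visit by treatment and overall using descriptive statistics". It also plans toxicity-grade shifts from baseline to each post-baseline visit. Vital signs (4.12.5), ECG values (4.12.6) and abnormal physical-examination findings (4.12.7) are summarized by visit too. SAP 4.11.1.2 rules out imputation for safety analyses.

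On patients who leave, Protocol 6.19 asks that "every effort should be made to schedule a final visit", with laboratory tests, ECG, vital signs and a complete physical examination. Under Protocol 3.4, patients who stop study drug early have end-of-treatment procedures as soon as possible, followed by the two follow-up visits.

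Finally, SAP 4.15 records that the trial was terminated early and that "the planned analyses have been changed to focus on safety assessments".

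**The concern.** A visit tolerance tells sites when to see a patient. An analysis window has a different job: to give every collected result a place in the tables. Using the first as the second means that a valid result taken a few days outside tolerance has no analysis visit. The same holds for an early-termination visit, which can fall on any day.

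The results at risk come from patients whose schedule broke down, including those who left. If a raised toxicity grade is recorded on a gap day, the shift table shows nothing for it. The by-visit summaries are then restricted to patients seen on schedule. That matters more here because, after SAP 4.15, the safety tables are the main product of the trial.

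**Working it through.** The documents state no coverage figure to reproduce, so the check is a direct count of days.

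**Inputs.** The windows come from SAP Table 1. The tolerances come from the protocol's Schedule of Assessments: ±3 days to Week 24 and ±5 days in follow-up.

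**Source of the windows.** Rebuilding each window as target ± tolerance matches 14 of the 15 post-baseline rows exactly. Week 1 differs: the tolerance gives Days 5 to 11, and the SAP uses Days 2 to 11.

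**Days covered.**
- Week 1: Days 2–11, 10 days
- Week 2: Days 12–18, 7 days
- Weeks 4 to 24: 11 windows × 7 = 77 days
- Total to Day 172: 10 + 7 + 77 = 94
- Weeks 28 and 32: 11 + 11 = 22, so the total to Day 230 is 116

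**Days in no window.**
- Days 2–172: 171 − 94 = 77, and 77/171 = 45%. These are eleven gaps of 7 days: 19–25, 33–39, and so on to 159–165.
- Days 173–191 (19 days) and 203–219 (17 days) add 36.
- Days 2–230: 77 + 36 = 113, and 113/229 = 49%.

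**Which visits are exposed.** For Weeks 4 to 22, a visit 4 to 10 days early or late lands in a gap. For Week 4 (target Day 29), 4 to 10 days late is Days 33 to 39. A Week 2 visit is exposed only on the late side, and a Week 1 visit has no gap beside it.

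**Patients who stop study drug.** Treatment windows repeat every 14 days, so a 28-day step from one gap leads into another while it stays within the treatment grid. For example, end-of-treatment procedures on Day 64 with follow-up every 4 weeks give nominal days 64, 92 and 120. These fall in the gaps 61–67, 89–95 and 117–123, so all three are unassigned.

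**Whether another rule recovers these results.** The nearest-to-target rule acts only among results already in the same analysis visit. The unscheduled-visit rule says when such a result may be used, but not which visit a gap-day result belongs to. No worst post-baseline or last-value summary is planned for laboratory or vital-sign data.

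**The case against.** The strongest reply is that calendar days are not data. Assessments cluster on scheduled visits, and every visit within tolerance of its target day is captured. This stands. A reader might infer from 49% that about half of the safety data is lost, and the documents do not support that. They give no count of out-of-tolerance or early-termination visits.

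A reader might also infer that an early-termination visit is more likely than not to be dropped. Restricting the count to Days 19–165 does give 77/147 = 52%, but that range starts and ends on gap days. Over the whole treatment part the same reasoning gives 45%. Both figures assume that such visits are equally likely on any day, which nothing in the documents supports; decisions to stop may well be made at or near a visit. Early-termination results on a covered day are kept.

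Nor do the documents show that early-termination visits were common because the trial was stopped. SAP 4.15 cites enrollment difficulties and a small sample; it does not say how many patients left early.

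The safety picture also has other routes. Adverse-event and AESI tables count subjects, not visits, and lose nothing. Clinically significant laboratory changes are to be treated as adverse events (Protocol 8.2), and AST/ALT above 5 times ULN is itself an AESI. SAP 4.12.6 plans a separate summary of abnormal ECG findings that is not stated to be by visit. Laboratory, vital-sign, ECG and physical-examination results all go into by-subject listings. All this limits the harm. It does not repair the by-visit and shift tables, which are the only planned group-level summaries of laboratory and vital-sign values.

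The SAP never says in words that out-of-window results are excluded, and its Table 1 has a nominal-visit column. But nothing says that nominal visit governs. If it did, the day limits would serve no purpose, and early termination would still have no row.

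Last, one set of midpoint windows for all parameters would put an early-termination ECG into rows such as Week 10, where no ECG is scheduled. This also stands, and it shapes the fix.

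**Conclusion.** The concern holds within limits. SAP Table 1 leaves 45% of Days 2–172 and 49% of Days 2–230 in no analysis visit, and no stated rule places a result from those days. Followed as written, the plan omits out-of-tolerance results and gap-day early-termination results from the by-visit laboratory, shift, vital-sign, ECG and physical-examination summaries.

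The day counts are exact and need no assumption. The exclusion is an inference from the table and the absence of any other rule. The number of results affected is unknown, and no hypothesis test depends on it. The change is still worth making: safety is now the focus, SAP 4.3.1 was itself revised on 15-Jun-22 after the termination update, and the repair is small.

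**What to change.** Make the post-baseline safety windows contiguous, cutting at the midpoint between consecutive target days at which each parameter is actually scheduled:
- Vital signs and physical examination (every visit): Week 1 Days 2–11, Week 2 Days 12–22, Week 4 Days 23–36, then 14-day windows to Week 22 (Days 149–162), Week 24 Days 163–183, Week 28 Days 184–211, Week 32 Days 212–230.
- Hematology and chemistry (Weeks 1, 4, 8, 12, 16, 20, 24, 28, 32): Days 2–18, 19–43, 44–71, 72–99, 100–127, 128–155, 156–183, 184–211, 212–230.
- ECG and urinalysis (Weeks 12, 24, 32): Days 2–127, 128–197, 198–230.

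Each set leaves 0 of the 229 post-baseline days unassigned. Keep the nearest-to-target rule, so a scheduled result on or near target is preferred when both exist. State that early-termination results go to the window they fall in. Add a last on-study value row to the by-visit tables and a worst post-baseline grade to the laboratory shift table.

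The cost is a revised table of days and a few sentences of SAP text; no new data are needed. The downside is that some values lie further from target: up to 14 days for a Week 4 laboratory result (Day 43 against Day 29). For ECG it can be much more, up to 85 − 2 = 83 days at Week 12, so the actual study day should be shown in the listings. The last-value row makes an early-leaver's final result visible whichever window it falls in.

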**Table 2. Analysis Window for CT Scan**

Nominal Visit	Analysis Visit	Target Study Day	Minimum Study Day	Maximum Study Day
Visit 2	Baseline	1	-30	1
Visit 15	Week 24 (End of Treatment)	169	166	172

**Table 3. Analysis Window for NPS, VAR-RS, SNOT-22, and TNSS**

Nominal Visit	Analysis Visit	Minimum Study Day	Maximum Study Day
Visit 2	Baseline	-7	-1
Visit 3	Week 1	1	8
Visit 4	Week 2	9	15
Visit 5	Week 4	23	29
Visit 7	Week 8	51	57
Visit 9	Week 12	79	85
Visit 11	Week 16	107	113
Visit 13	Week 20	135	141

Visit 15	Week 24 (End of Treatment)	163	169
Visit 17	Week 32 (End of Study)	219	225

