6.15 Visit 15 (End of Treatment) (Study Day 169 ± 3 days/Week 24)

The following assessments and procedures should be completed in the order given below, if possible:

- Review and record changes in of concomitant medications
- Vital sign measurements
- Brief physical exam
- Review of patient diary and NPIF data
- Record body weight
- CT scan (only required for subjects that are enrolled at Study Sites that are approved and qualified to perform CT Scans)
- NCS assessment

Suzhou Connect Biopharmaceuticals, Ltd

Protocol CBP-201-WW003

Investigational Drug: CBP-201

21 December 2021

- EQ-5D-5L assessment
- VAS-rhinosinusitis assessment
- SNOT-22 assessment
- TNSS assessment
- UPSIT assessment of smell
- Nasal endoscopy and NPS scoring
- Pulmonary Function Tests (Spirometry) for patients with comorbid asthma only
- Healthcare resource utilization questionnaire
- 12-lead ECG
- Urine pregnancy test
- Safety laboratory samples (hematology, serum chemistry, urinalysis)
- PK blood sample (predose)
- PD blood sample (predose)
- ADA blood sample (predose)
- Administer study drug
- Injection site assessment
- Dispense optional take-home rescue medications (albuterol/salbutamol) to patients with asthma, if needed. Remind patients to document the use in their patient diary.
- AE review and recording

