**Table 4. Analysis Window for Efficacy Parameters – Weekly average**

Nominal Visit	Analysis Visit	Minimum Study Day	Maximum Study Day
Visit 2	Baseline	-7	-1
Visit 3	Week 1	1	8
Visit 4	Week 2	9	15
Visit 5	Week 4	23	29
Visit 6	Week 6	37	43
Visit 7	Week 8	51	57
Visit 8	Week 10	65	71
Visit 9	Week 12	79	85
Visit 10	Week 14	93	99
Visit 11	Week 16	107	113
Visit 12	Week 18	121	127
Visit 13	Week 20	135	141
Visit 14	Week 22	149	155
Visit 15	Week 24 (End of Treatment)	163	169
Visit 16	Week 28	191	197
Visit 17	Week 32 (End of Study)	219	225

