**Table 5. Analysis Window for Other Efficacy Parameters**

Nominal Visit	Analysis Visit	Minimum Study Day	Maximum Study Day
Visit 2	Baseline	-7	-1
Visit 3	Week 1	1	8
Visit 4	Week 2	9	15
Visit 5	Week 4	23	29
Visit 6	Week 6	37	43
Visit 7	Week 8	51	57
Visit 8	Week 10	65	71
Visit 9	Week 12	79	85
Visit 10	Week 14	93	99
Visit 11	Week 16	107	113
Visit 12	Week 18	121	127
Visit 13	Week 20	135	141
Visit 14	Week 22	149	155

Visit 15	Week 24 (End of Treatment)	163	169
Visit 16	Week 28	191	197
Visit 17	Week 32 (End of Study)	219	225

If more than one assessment is available within the same analysis visit, the assessment with closest study day to the target study day will be reported for the analysis window. If two observations exist with the same distance to the target study day, then the first observation will be used.

Unscheduled visit will not be used in the analysis if scheduled visit is available. Unscheduled visit will be used in the analysis only if scheduled visit is not available.

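### SAP Table 3 sets Week 24 NPS at Days 163-169, so three of the seven days on which the protocol permits the Week 24 endoscopy (170-172) map to no analysis visit

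*SAP*

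**What the plan says.** The protocol places the Week 24 endoscopy at "Visit 15 (End of Treatment) (Study Day 169 ± 3 days/Week 24", and the procedures listed for that visit include "Nasal endoscopy and NPS scoring". The permitted days are therefore 166 to 172.

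SAP section 4.3.1 assigns assessments to analysis visits by study day, with a separate table for each group of measures. NPS is in Table 3, titled "Table 3. Analysis Window for NPS, VAR-RS, SNOT-22, and TNSS". Its Week 24 row reads "Week 24 (End of Treatment) 163 169", and the next row is Week 32, Days 219 to 225. Tables 1 (safety) and 2 (CT) give Week 24 as Days 166 to 172, with a target day of 169. Table 4, for weekly diary averages, has the same Days 163 to 169 as Table 3.

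Two selection rules follow Table 5. When one analysis visit holds several assessments, "the assessment with closest study day to the target study day will be reported for the analysis window". An unscheduled visit is used only when no scheduled one is available. Neither rule deals with a scheduled assessment whose day lies in no row.

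**The concern.** NPS is one reading at one clinic visit. A window for such a measure should at least cover the days on which the visit may take place. The Table 3 rows are instead 7-day look-backs ending on the target day (Week 1 spans 8 days), and they equal the Table 4 rows for the same weeks. That shape suits a diary average over the week before the visit. It does not suit a single endoscopy: it admits Days 163 to 165, when the protocol permits no Week 24 visit, and leaves out Days 170 to 172, when it does.

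A patient seen on Day 171 would then have Week 24 laboratory and CT results but no Week 24 NPS. NPS at Week 24 is a co-primary endpoint. Under SAP 4.15, descriptive statistics for the co-primary endpoints are the only efficacy summary left, in a sample that the SAP itself calls small. A descriptive mean has no model behind it to recover omitted values.

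**Working it through.** **Common scale.** The protocol calls the baseline visit Study Day 1. SAP 4.3.1 counts from the first dose as Day 1 and has no Day 0. The day numbers can be compared directly.

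**Day-by-day comparison for the visits with endoscopy.** Permitted days are the protocol target plus or minus the tolerance. Each was checked against every row of Table 3.

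| Visit | Protocol | Permitted days | Table 3 row | Permitted days in no row |
|---|---|---|---|---|
| Week 2 | 15 ± 3 | 12-18 | 9-15 | 16-18 (3 of 7) |
| Week 8 | 57 ± 3 | 54-60 | 51-57 | 58-60 (3 of 7) |
| Week 16 | 113 ± 3 | 110-116 | 107-113 | 114-116 (3 of 7) |
| Week 24 | 169 ± 3 | 166-172 | 163-169 | 170-172 (3 of 7) |
| Week 32 | 225 ± 5 | 220-230 | 219-225 | 226-230 (5 of 11) |

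None of the days in the last column falls in another Table 3 row. With a Week 24 row of 166-172, all seven permitted days map to Week 24.

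**The plan's sample size, to fix the denominator.** SAP 4.14 gives SD 2.1, difference 1.3, two-sided alpha 0.05 and power 80%. Per group, n = 2 × (1.960 + 0.842)² × 2.1² / 1.3² = 2 × 7.85 × 4.41 / 1.69 ≈ 41. Allowing for 15% dropout, 41 / 0.85 = 48.2, rounded up to 49, or 147 in total. Both figures reproduce. The number expected to have a Week 24 reading is 41 per group, since 49 already includes dropouts.

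**Share of on-time visits that fall late.** The documents give no distribution of visit days, so these are assumptions:

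- Even over the seven days: 3/7 = 42.9%; 41 × 0.429 = 17.6, about 18 per arm.
- Triangular around Day 169, weights 1, 2, 3, 4, 3, 2, 1: (3 + 2 + 1)/16 = 37.5%; 41 × 0.375 = 15.4, about 15 per arm.
- Half exactly on Day 169 and the rest symmetric: 25%; 41 × 0.25 = 10.25, about 10 per arm.

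**The case against.** The strongest reply is that the SAP nowhere says an out-of-window value is excluded. Every window table has a Nominal Visit column, and the unscheduled-visit rule shows that the SAP also knows visits by their label. A programmer could reasonably keep a Visit 15 endoscopy on Day 171 as Week 24. This stands as a limit on certainty: exclusion follows from applying the day limits as written and is not stated. It does not remove the problem. The closest-day rule works only inside an analysis visit and needs a target day, which Table 3 lacks. The unscheduled-visit rule ranks types of visit and assigns no week. Two programmers could therefore report different n for a co-primary endpoint.

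A reader might infer that the trial's power or its co-primary conclusion is at risk. The documents do not support that. SAP 4.15 drops all hypothesis tests and all sensitivity and subgroup analyses. NCS is a diary average for which the Table 4 look-back is appropriate, so the affected patients stay in the NCS summary. SNOT-22, TNSS and VAS-RS are now only listed. SAP 4.11.2.1 plans a by-subject listing of the primary efficacy data, so the NPS readings need not vanish from the report. A reader might also apply the late fractions to 49 per arm; that overstates the loss, because 49 includes the dropout allowance.

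**Conclusion.** The inconsistency is real. Applied by study day, SAP Table 3 leaves 3 of the 7 permitted Week 24 days, and 5 of the 11 at Week 32, without an analysis visit for NPS. That much is exact and needs no assumption. On-schedule readings on those days would be left out of the Week 24 NPS summary unless someone maps them by visit label, which the SAP does not instruct.

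How many patients this affects is unknown. With 25% to 43% of visits late, it is about 10 to 18 of 41 evaluable patients per arm at planned size. The trial stopped early, so only the percentages carry over. The consequence is confined to the n, mean and SD of the descriptive NPS summary. It should still be settled, because it decides which protocol-compliant readings of a co-primary endpoint are counted.

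**What to change.** In SAP Table 3, and for the visit-based measures in Table 5, replace every post-baseline row with the windows that Table 1 already uses: Week 1, 2-11; Week 2, 12-18; Week 4, 26-32; Week 8, 54-60; Week 12, 82-88; Week 16, 110-116; Week 20, 138-144; Week 24, 166-172; Week 32, 220-230. These equal the protocol visit windows, except that Week 1 opens at Day 2 where the protocol's Day 8 ± 3 gives 5-11.

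Change all rows together. Moving Week 2 to 12-18 while Week 1 stays at 1-8 would leave a permitted Week 1 visit on Days 9-11 in no row, which matters for the questionnaires.

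Add the target-day column that the closest-day rule needs. State that a scheduled assessment outside every window is assigned to its nominal visit. Keep the 7-day look-back only in Table 4, for diary averages.

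The cost is a table edit and a programming parameter, with no new data. The revision history shows that section 4.3.1 was already updated in version 1.4, after the early-termination update, so a further change should be documented as made before unblinding.
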